3.5 Secondary endpoints/outcomes

The secondary objective is feasibility (completeness and summary statistics) of recording the following measures at baseline:

Demographics and the Alcohol, Smoking and Substance Involvement Screening Test (ASSIST)

Page 25 of 60

And of the following measures at baseline (where applicable), 8 weeks, 16 weeks, 6 months, and 12 months post-baseline:

Height, weight, BMI, ED psychopathology questionnaires- (RCADS, EDE-Q, BAVQ-R, SREBQ), General psychopathology assessments and questionnaires-(DASS, RCDADS, Y-BOCS, C-SSRS), Health economic and quality of life assessments (EQ-5D-Y, CAA-SUS, , EDSIS,) olanzapine plasma levels (8 weeks only), Physical examination measures, ECG, laboratory parameters, ESS, ESS-CHAD and quality of adverse events reporting (UKU-SERS).

Also to assess willingness to participate in an RCT (blinded, placebo-controlled).

3.6 Exploratory endpoints/outcomes

3.6.1. Treatment as usual

It is unclear whether TAU can be defined according to current guidelines. Therefore, we will use a checklist to document the types of TAU elements patients received, their frequency, length and setting. We will also record Concomitant Medications to document the different medications patients are taking for their anorexia as well as their various co-morbidities and to explore whether any commonly taken additional medications affect the action of olanzapine in this population (drug-drug interactions).

3.6.2. Patients experience of recruitment and treatment

Patient experience of recruitment and treatment, acceptability and reasons for adherence and nonadherence will be ascertained in qualitative interviews which will be performed, transcribed and analysed.

3.6.3 Change in measures over time

Change in the measures as listed in section 3.5 will be explored/described to inform a future definitive study design.

3.7 Schedule of events

Synopsis and schedule of OPEN outcomes/assessment tools in the feasibility study. The superscript numbers indicate, who will perform the scheduled assessments: ¹Resercher, ²The study participant's clinical treatment team, ³Qualitative Researcher. * if procedure is performed on the day of the Screening visit, it does not need to be repeated; items highlighted in green are standard care procedure.

Methods/Assessments	Screening	Baseline	Igniighted in Assessment at			Assessment at
		Assessment (≤ 7-10 days following Screening)	8 weeks (±7 days)	16 weeks (±7 days)	6 months (±7 days)	12 months (±7 days)
Informed Consent	X1	ocreening)				
Clinical Examinations						
- Inclusion/Exclusion Criteria	X1					
 Psychiatric and physical examination 	X ^{1,2}		X1.2	X ^{1,2}	X ^{1,2}	X ^{1,2}
 Weight, height, blood pressure (BP), body temperature 	X ^{1,2}	X ^{1,2*}	X ^{1,2}	X ^{1,2}	X ^{1,2}	X ^{1,2}
- Laboratory parameters (Electrolytes and salt/water balance - Kidney function, Liver	X ^{1,2}		X1.2	X ^{1,2}	X ^{1,2}	X ^{1,2}
function Blood count/bone marrow, Fasting glucose and lipid profile)						
- Electrocardiogram (ECG)	X ^{1,2}		X1.2	X ^{1,2}	X1.2	X1.2
- Concomitant Medications	X1	X1*	X1	X1	X1	X1
- Serum Pregnancy Test	X1,2		X1,2	X ^{1,2}	X1,2	X1.2
IMP dispensing		X1.2	X1.2	X ^{1,2}	X1.2	
Screening for Drug or Alcohol Abuse Disorders						
 Alcohol, Smoking and Substance Involvement Screening Test (ASSIST) 		X1				
Treatment as Usual						
 Treatment elements checklist 		X1	X1	X1	X1	X1
Adherence measures						
- Olanzapine plasma level			X ^{1,2}			
- Pill count			X1.2	X ^{1,2}	X ^{1,2}	X ^{1,2}
AE recording/reporting			X1	X1	X1	X1
 UKU Side Effects Rating Scale 			X1	X ¹	X1	X ¹
Eating Disorders Psychopathology						
 Eating Disorder Examination-Questionnaire (EDE-Q) 		X1	X1	X1	X1	X1
 Revised Beliefs about Voices Questionnaire (BAVQ-R) 		X1	X1	X1	X1	X ¹
 Self-regulation of Eating Behaviour Questionnaire (SREBQ) 		X1	X1	X1	X1	X ¹
General Psychopathology						
- Depression Anxiety Stress Scales (DASS/RCADS)		X1	X1	X1	X1	X1
- Yale-Brown Obsessive-Compulsive Scale (Y-BOCS/CY-BOCS)		Х	Х	X1	X1	X1
- Columbia Suicide Severity Rating Scale (C-SSRS)		X1	X1	X1	X1	X1
Rating and Documentation of Side Effects						
- Epworth Sleepiness Scale (ESS/ESS-CHAD)		X1	X1	X1	X1	X1
Health Economy and Quality of Life						
- EQ-5D-Y™		X1			X1	X1
 Child, Adolescent and Adult Service Use Schedule (CAA-SUS) 		X1			X1	X1
- Eating Disorders Symptom Impact Scale (EDSIS)		X1			X1	X1
Qualitative Research						
 Patient experience: Interview with those who consent to trial participation 		X ³				
 Patient experience: Interview with those who declined to participate in trial 		X3				
 Experience of treatment and the trial (including adherence/nonadherence) 				X3		
Questions on RCT						
 Willingness to take part in an RCT (double-blind) 		X1			X1	X1

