3.2 Secondary objectives

Secondary objectives are to test the feasibility of data collection procedures (completeness and summary statistics) for the following measures:

Page 21 of 60

- Measures at baseline (demographics, smoking, alcohol, and substance abuse)
- Body weight and BMI
- Eating disorder psychopathology
- General psychopathology
- Health economic and quality of life assessment completed by both participants and their carers
- Drug adherence (to examine different methods to measure adherence (questionnaire, pill count, olanzapine plasma level)
- Drug safety (to examine the quality of reporting of adverse events)

Also to use qualitative methods to assess willingness to participate in a blinded, placebo-controlled RCT

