3.3 Outcome measures/endpoints

3.3.1. Feasibility of questionnaires and assessments

We will assess the applicability of potential future RCT outcomes, assessment measures and completion of assessments. Questionnaires not completed in >25% will not be included in a potential application for a randomized pilot study or full RCT following this feasibility. This feasibility study includes full assessments at baseline, after 8 weeks, after 16 weeks, after 6 months and after 12 months. The assessments will be conducted by the researcher with the support of the patients' clinical service teams. Qualitative interviews will take place at baseline and after 16 weeks. Furthermore, patients who refuse to enter the study will also be offered the opportunity to participate in a qualitative interview aimed at understanding their reasons for refusing to participate in the OPEN study. They will be conducted by the qualitative researcher; see flow chart.

During study-related activities, the intake of olanzapine and the study assessments, 12- to 15-year-old children will be accompanied by a trusted adult, which may be a parent, carer or a clinical staff member entrusted with the clinical care of the patient.

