3.4 Primary endpoint/outcome

Primary objective: feasibility

Primary endpoints: Assessing the proportion of patients in different settings, examining different methods to measure adherence (questionnaire, pill count, olanzapine plasma level). Important measurement time points are the baseline and 12 months after baseline.

Summary statistics will be presented on the following for feasibility and may include estimation of confidence intervals:

Patients approached, screened and included in the study

Adherence, completed physical assessments (including BMI measurement) and questionnaires

Willingness to take part in an RCT

Elements that constitute TAU

Summary statistics on psychopathology, general psychopathology and quality of life assessments and change in BMI will also be reported.

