7.2 Consent

The CI will have overall responsibility for the conduct of research. The CI will ensure that any person delegated responsibility to participate in the informed consent process is duly authorised, trained and competent to participate according to the ethically approved protocol and principles of Good Clinical Practice (GCP) and Declaration of Helsinki.

Informed consent will be obtained prior to the participant undergoing the baseline assessments.

Written consent will be taken by the members of the research team at each site. The Patient Information and Consent forms will be given to the participants and ample time will be given for the participants to review and complete the forms and for any questions to be answered. One copy of the signed consent forms will be given to the patient, one copy will be kept in the patient medical notes and one copy will be filed in the Site File.

The right of a participant to refuse participation without giving reasons must be respected, and the participant will remain free to withdraw at any time from the trial without giving reasons and without prejudicing his/her further treatment and will be provided with a contact point where he/she may obtain further information about the trial. This contact point will be the researcher and the CI.

Data and samples collected up to the point of withdrawal will only be used after withdrawal if the participant has consented for this. This is explained in the information sheet and specified in the consent form. Patients under 16 years old will be required to assent to take part in the trial and a consent from a parent/legal guardian will be obtained. Participants who turn 16 years old during the study will be required to consent, and it is the responsibility of the PI to ensure this is done in a timely manner. The PI will take responsibility for ensuring that all participants are protected and participate voluntarily in an environment free from coercion or undue influence.

We will only include patients who can read and write in English.

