7.7 Trial assessments

Trial assessments will take place 8 weeks, 16 weeks, 6 months, and 12 months after baseline with an appointment of approximately 3 hours and will take place in person at trial sites. They include:

Clinical Examinations

- Psychiatric and physical examination
- Weight, height, blood pressure (BP), body temperature
- Laboratory parameters
- Body temperature
- Electrocardiogram (ECG)
- Treatment as Usual check
- Treatment elements checklist
- Concomitant Medications

Page 35 of 60

Adherence measures

- Olanzapine plasma level
- Pill count

Psychopathology

- Eating Disorder Examination-Questionnaire (EDE-Q)
- Depression Anxiety Stress Scales (DASS/RCADS)
- Revised Beliefs about Voices Questionnaire (BAVQ-R)
- Self-Regulation of Eating Behaviour Questionnaire (SREBQ)
- Yale-Brown Obsessive-Compulsive Scale (Y-BOCS/CY-BOCS)
- Columbia Suicide Severity Rating Scale (C-SSRS)

Rating and Documentation of Side Effects

- Epworth Sleepiness Scale (ESS/ESS-CHAD)
 - UKU- Side Effects Rating Scale (UKU-SERS)

Health Economy and Quality of Life

- EQ-5D-YTM
- Child, Adolescent and Adult Service Use Schedule (CAA-SUS)
- Eating Disorders Symptom Impact Scale (EDSIS)

Qualitative Research

- Experience of treatment and the trial, including motivation for adherence/nonadherence (after 16 weeks only)
- Carers/parents will be given an opportunity to contribute at the 16 week qualitative interview with the participants' consent.

Questions on RCT

• Willingness to take part in an RCT (double-blind; after 6 and after 12 months only)

For the justification of these data, see section 3. Section 3.7. provides an overview of all assessments and when they will take place.

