7.9 Qualitative assessments

Patient experience of recruitment and treatment: Patient experience of recruitment and treatment, treatment acceptability and reasons for adherence or non-adherence will be ascertained in qualitative interviews which will be performed, transcribed, and analysed.

We will conduct individual qualitative interviews in a subgroup (N=30) of young people with AN who either agree (N=20) or decline (N=10) to participate in the OPEN feasibility study. Interviews will be

Page 36 of 60

conducted virtually or face-to-face based on the participants preference. Interviews will examine the decision-making process and the perceived risks and advantages of taking olanzapine within the study.

Those who are recruited to OPEN will be interviewed at baseline and after the 16-week assessment point about their experiences of olanzapine treatment, participating in the study, including beliefs about side effects, acceptability and adherence, the perceived burden of completing outcome measures and attitudes towards randomisation in a future clinical trial. We will interview people who have adhered to olanzapine as well as people who have dropped out. Patients who decline to participate in the main study but have consented to take part in the interviews will participate in one interview at baseline. The qualitative researcher will aim for 'empathic neutrality', posing open and non-leading questions that invite participants to recount their experiences of the study and treatment from their perspective.

Purposive sampling will be conducted based on gender, age, recruitment source, BMI at baseline and adherence to explore a range of perspectives.

Qualitative data will be analysed using the Framework Approach [85] to facilitate analysis within and between individual cases and groups of participants. The thematic framework will draw on a priori issues around the acceptability of the intervention and design study, but also be responsive to emergent themes. [name] will supervise a qualitative researcher who will get in contact with approached and recruited patients. All qualitative interviews in the UK will be carried out by the UK qualitative researcher (TBA). Qualitative data evaluation will be performed in cooperation with the qualitative research performed in [name] and [name] will consult with each other about the qualitative research performed in both countries.

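### Willingness to join a blinded, placebo-controlled RCT is asked only of patients who accepted open-label olanzapine, so the result describes a selected part of the RCT's recruitment pool

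*Protocol*

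**What the plan says.** Protocol section 3.2 sets the objective: "Also to use qualitative methods to assess willingness to participate in a blinded, placebo-controlled RCT". Section 3.5 repeats it as an outcome: "Also to assess willingness to participate in an RCT (blinded, placebo-controlled". Section 3.4 lists "Willingness to take part in an RCT" among the feasibility items to be summarised, possibly with confidence intervals.

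The schedule of events (3.7) has a row for the question, "Willingness to take part in an RCT (double-blind", at baseline, 6 months and 12 months, assigned to the researcher. Section 7.6.3 repeats the baseline asking, and section 7.7 gives the later ones: "Willingness to take part in an RCT (double-blind; after 6 and after 12 months only". On who reaches baseline, section 7.2 says: "Informed consent will be obtained prior to the participant undergoing the baseline assessments". Sections 4 and 7.3 make clear that every participant knowingly receives olanzapine and that there is no placebo or comparator.

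Patients who decline are offered one interview at baseline, held by the qualitative researcher. Section 3.3.1 describes it as "aimed at understanding their reasons for refusing to participate in the OPEN study". Section 7.9 plans 20 interviewees who agree to join and 10 who decline, and says of both: "Interviews will examine the decision-making process and the perceived risks and advantages of taking olanzapine within the study". Views on being randomised in a later trial are named as a topic only for recruited patients. Section 7.9 covers them at baseline and after 16 weeks; section 10.3.5 places the topic after the 16-week assessment.

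**The concern.** A placebo-controlled RCT would approach all eligible patients, including those who would refuse a study in which olanzapine is certain. Refusing a known drug is not the same as refusing randomisation, and accepting a known drug does not imply accepting the chance of placebo. Under this plan only accepters answer the RCT question, and two of the three askings come after they have started the drug.

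Willingness is a stated outcome of a study whose purpose is to inform a definitive RCT. If the accepters' figure is read as willingness among all patients approached, it could mislead in either direction. Enrolling more participants would not narrow the gap, and no later analysis can recover answers that were never collected.

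**Working it through.** **Who is asked what**

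| Group | Fixed RCT question | Views on randomisation in interview | Stated interview content |
|---|---|---|---|
| Accepters | Baseline, 6 and 12 months (3.7, 7.6.3, 7.7) | Baseline and 16 weeks (7.9); after 16 weeks (10.3.5) | Decision to join; views of olanzapine; experience of treatment and study |
| Decliners | Not scheduled | Not named | Reasons for refusing OPEN; decision process; views of olanzapine (3.3.1, 7.9, 10.3.5) |

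The baseline column of the schedule holds the decliner interview as a separate row, assigned to the qualitative researcher. The RCT question is assigned to the researcher. With consent required before baseline assessments, the plan does not put the question to decliners.

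**The plan's own precision, as a yardstick**

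Section 10.1 gives margins for adherence with 55 patients: 12.2% at a rate of 70% and 13.3% at 50%. No figure is given for willingness. The formula is 1.96 × √(p(1−p)/m).

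- With m = 55: 12.11 and 13.21 points.
- With m = 54 (n − 1): 12.22 and 13.34 points, which match the stated values.
- The same formula at p = 60%: 1.96 × √(0.24/54) = 13.1 points.

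**How far the accepters' figure could lie from the approached pool**

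Let a be the share who accept OPEN, w_acc the willingness among accepters and w_dec that among decliners.

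- Willingness in the pool = a × w_acc + (1 − a) × w_dec.
- Gap (accepters minus pool) = (1 − a) × (w_acc − w_dec).

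The documents give none of these three quantities. All values below are assumptions: w_acc = 60%, w_dec from 20% to 80%, a = 30%, 50% or 70%.

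| a | Pool, w_dec = 20% | Pool, w_dec = 80% | Gap in points |
|---|---|---|---|
| 30% | 0.18 + 0.14 = 32% | 0.18 + 0.56 = 74% | +28 to −14 |
| 50% | 0.30 + 0.10 = 40% | 0.30 + 0.40 = 70% | +20 to −10 |
| 70% | 0.42 + 0.06 = 48% | 0.42 + 0.24 = 66% | +12 to −6 |

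The study would report 60% in every row. At 30% acceptance both ends exceed the 13.1-point margin; at 50% only the upper end does; at 70% neither does. The gap is zero only if decliners are as willing as accepters.

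**What ten decliners could add**

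If 5 of 10 said yes, the exact 95% interval would be 19% to 81%. That is nearly as wide as the assumed range, so the yield is reasons and rough direction, not a proportion.

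**The case against.** The strongest reply has four parts.

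- **The objective is qualitative.** Section 3.2 says so, decliners are among those interviewed, and section 7.9 describes open questions and an analysis open to new themes. A protocol need not contain the interview guide, so a decliner may in fact be asked about an RCT. This stands in part: one cannot say that decliners will never be asked. But the stated aims and topics leave the matter out for decliners while naming it for accepters, and section 3.4 also plans a numerical summary, which the fixed question supplies from accepters alone.
- **No RCT recruitment rate is promised.** This stands. The protocol does not say that the answers will be converted into expected uptake or pooled across visits, and section 10.3.2 leaves willingness out of its own list. The risk lies in how the figure will be read.
- **Change over time is already planned.** Section 3.6.3 covers the measures in section 3.5. This also stands, but it does not say which answer is the main one.
- **The ranges are assumed.** True. They show only what an unmeasured group could do.

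A reader might go further and infer that the answers come from outside the RCT's recruitment pool. The documents do not support that: at baseline the respondents are eligible non-responders to usual treatment, hence part of that pool. Nor are views on randomisation explored only at 16 weeks, since section 7.9 also covers baseline. A reader might also apply the 28% dropout in section 1.3 to the 12-month answers. That figure pools intervention arms of other trials, and section 7.10 seeks to keep following patients who stop olanzapine.

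**Conclusion.** The point holds as a limited design gap with a cheap remedy. Followed as written, the plan yields willingness among open-label accepters, which is a selected part of an RCT's recruitment pool. The direction of bias is unknown: accepters may be readier for trials in general, or less ready to risk placebo. Under the assumed values the accepters' figure differs from the pool by between +28 and −14 points at 30% acceptance, and by between +12 and −6 at 70%.

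The 6- and 12-month answers carry a further limit, because they come from patients who have started open-label treatment. The baseline answer, if taken before the first dose, remains useful provided its population is stated. It would be too strong to say that the objective goes unanswered, or that adding decliners would produce an RCT recruitment rate.

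**What to change.** - **Sections 3.3.1, 7.9 and 10.3.5:** add to the decliner interview the same fixed RCT-willingness question that participants receive. Record it under that interview's own consent and outside the EDC, because section 11.1 bars EDC entry without signed trial consent.
- **Sections 3.4 and 3.5:** name the baseline answer, taken before the first dose, as the main willingness result, and state that it applies to patients who accepted open-label olanzapine. The schedule dispenses the drug at baseline, so the order within that visit should be fixed.
- **Reporting:** give decliners' answers separately and descriptively, as counts with the reason (objection to the drug, to placebo or to research). Report the 6- and 12-month answers only as change after open-label experience.

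The cost is one question in an interview already planned and a few sentences of text. No treatment, visit or sample size changes. The downside is that about ten purposively sampled decliners can show why, and roughly whether, they differ from accepters, but cannot give a precise proportion or an RCT recruitment rate.

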4 TRIAL DESIGN

The design of this feasibility study is open treatment of 55 patients with olanzapine for 12 months. Participants will be examined at baseline, and at 8 weeks, 16 weeks, 6 months and 12 months after start of treatment. This is a one-arm open treatment design, there is no placebo and no comparator.

5 TRIAL SETTING

This a multicentre trial. There are no specific site requirements other than what is standard in NHS eating disorders services.

- A medical doctor to prescribe olanzapine and to perform the physical examination.
- The facility to take blood for routine laboratory parameters and to determine olanzapine plasma levels.
- An ECG to measure QTc time.

The researcher employed for this study and the CI will keep a list of sites participating in the trial. Recruitment at specialist CAMHs and adult eating disorder units in inpatient/outpatient settings at NHS sites to ensure generalisability (different treatment setting, degree of severity, chronicity).

The consultant psychiatrist involved in the clinical treatment of patients will inform the trial team about a potential patient and ask the patient whether they can be contacted online if necessary. Obtaining informed consent and inclusion into the study will take place on site by a member of the research team.

6 PARTICIPANT ELIGIBILITY CRITERIA

Patient group: 55 adolescent and young adults (of all sexes/genders) with AN not responding to TAU, according to NICE, for at least a month of treatment. Our age range starts from 12 years as, in a comparable published trial [28] and a published study proposal [83] in adolescent patients with AN, the minimum age was 12 years for safety reasons. According to olanzapine's SmPC, olanzapine is currently not recommended for use in children and adolescents below 18 years of age due to a lack of data on safety and efficacy. However, as stated in the NIHR HTA call 16/97 "Antipsychotics for anorexia nervosa", olanzapine is widely used in people with AN between 12 and 24 years even though it is not licensed and studies testing its safety are lacking. One purpose of this feasibility is to test, whether a study investigating the safety of olanzapine in this patient group is feasible. The main concern when prescribing olanzapine in adolescents with schizophrenia is weight gain and the consequences of weight gain such as lipid disturbances. In people with AN, however, this weight gain is the intended therapeutic effect, as weight gain is necessary for patients' medical safety and to be able to take part in psychotherapeutic measures.

